### **5.1.3 DOSE-LIMITING TOXICITIES**

Subjects in both dosing schedules will be evaluated for DLTs according to the National Cancer Institute-Common Terminology Criteria for Adverse Events ([NCI-CTCAE](#)), Version 4.03 during the 28-day period of Cycle 1 combination therapy. Intrasubject dose escalation to the RP3D may be permitted once that dose has been determined and after a discussion has occurred between the treating physician and **the Sponsor's** study medical monitor. The decision to escalate to the next higher dose of oprozomib in **this** study will be based on an assessment of study drug-related DLTs during Cycle 1 by the CSRC. The CSRC consists of investigators, the **Sponsor's** study medical monitor, and **the Sponsor's** drug safety representative. Each subject in the cohort under review will be discussed and assessed. Once all data have been presented, the CSRC will decide on the most appropriate course of action regarding dose escalation based on guidance in [Section 5.1](#).

Study drug is defined as the combination of oprozomib, pomalidomide, and dexamethasone. Study drug-related is defined as a reasonable likelihood of clinical causality based on time of event, biology, dechallenge improvement and that the AE was not likely explained by the subject's clinical state, underlying disease, concomitant medication, or study/nonstudy procedure. Definition of DLTs and additional details are provided in [Section 10.5](#).

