### 10.1 OPROZOMIB TREATMENT ADMINISTRATION

Oprozomib ER Tablets will be administered in single daily doses. Oprozomib will be administered orally, once daily for 5 consecutive days every other week ([5/14 schedule] ie, on Days 1–5 and 15–19) or once daily for 2 consecutive days of every week ([2/7 schedule] ie, on Days 1, 2, 8, 9, 15, 16, 22, and 23) of each 28-day treatment cycle. Treatment with oprozomib will continue until disease progression, unacceptable toxicity, or study treatment discontinuation for any reason. On days on which oprozomib and dexamethasone are administered concurrently, dexamethasone should be taken at least 30 minutes before oprozomib. Subjects are to be informed not to break, chew, or crush the Oprozomib ER Tablets.

In the dose-escalation and dose-expansion portions of the study, subjects who permanently discontinue pomalidomide or oprozomib may continue on study. If both pomalidomide and oprozomib are permanently discontinued, study treatment will be discontinued but the subject will be followed until disease progression.

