### 13.2 CAUSALITY

A suspected adverse event means any AE for which there is reasonable possibility that the study drug caused the AE. “Reasonable possibility” means that there is evidence to suggest a causal relationship between the drug and the AE.

The relationship of the AE to the study drug should be assessed using the following criteria:

YES; the event is suspected to be related if:

- There is a clinically plausible time sequence between the AE onset and administration of study treatment; and/or
- There is a biologically plausible mechanism for the study treatment to cause or contribute to the AE; and/or
- The event improves or diminishes upon withdrawal of the study drug without the initiation of any specific treatment for the event (dechallenge) and/or recurs or worsens with rechallenge (when clinically feasible); and/or
- The AE cannot be reasonably attributed to concurrent or underlying illness, other drugs, or procedures

NO; the event is not suspected to be related if:

- The AE is more likely to be explained by the subject’s clinical state, underlying disease, or concomitant medical, study, or nonstudy procedure; and/or
- The time of occurrence of the AE is not reasonably related to administration of study treatment; and/or
- The event is not related to the investigational product(s)

In the event of a possible drug-related AE, the investigator should to the best of his/her ability assess its relationship to each of the study drugs: oprozomib, pomalidomide, and dexamethasone.

Approved

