7.6.1 Adverse Events

Each reported AE term will be mapped to a preferred term (PT) and a system organ class (SOC) using the Medical Dictionary for Regulatory Activities (MedDRA).

Treatment-emergent adverse events (TEAEs) are defined as AEs that start on or after the first day of study treatment and within 30 days of the last day of study treatment. An AE that is present before the first administration of study treatment and subsequently worsens in severity during treatment is also considered to be treatment-emergent.

Adverse events will be summarized based on the number (%) of subjects experiencing events by MedDRA system organ class and preferred term. The denominator for the

percentage will be based on the number of subjects at in the Safety Population (i.e., those that received at least one dose of study drug).

A subject reporting the same AE more than once will be counted only once when calculating 1) within a given system organ class, and 2) within a given system organ class and preferred term combination. For such cases, the maximum National Cancer Institute (NCI; US) - Common Terminology Criteria for Adverse Events toxicity grade and strongest causal relationship to study treatment for the event will be used in the incidence calculations. AEs will also be summarized by severity and by relationship to study drug.

An overall summary of TEAEs will summarize the number (%) of subjects

- with at least one TEAE
- with at least one treatment-related TEAE, defined as related to OPZ or DEX
- with at least one grade 3 or higher TEAE
- with at least one treatment-related grade 3 or higher TEAE, either OPZ or DEX
- with at least one serious AE
- with TEAE leading to discontinuation of study drug, either OPZ or DEX
- with TEAE leading to discontinuation of OPZ
- who died within 30 days of last dose of study drug

Summaries of the following TEAEs will be provided by SOC and/ or PT unless otherwise noted:

- all TEAEs
- all TEAs (PT)
- TEAEs by maximum severity
- TEAEs grade 3 or higher (PT)
- treatment-related adverse events (OPZ, POM, DEX, and study drug)

- serious TEAEs
- TEAEs that led to permanent discontinuation of study drug (OPZ, POM, DEX and study treatment)

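### Three of the eight rows in the SAP's overall adverse-event summary leave out pomalidomide, against the protocol's three-drug definition of study drug and the SAP's own detailed tables

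*SAP*

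**What the plan says.** The overall summary in SAP 7.6.1 has eight rows, and three of them are tied to named drugs in the same way:

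- subjects "with at least one treatment-related TEAE, defined as related to OPZ or DEX"
- subjects "with at least one treatment-related grade 3 or higher TEAE, either OPZ or DEX"
- subjects "with TEAE leading to discontinuation of study drug, either OPZ or DEX"

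A fourth row, discontinuation of oprozomib, is a single-drug row by design. The other four rows (any event, grade 3 or higher, serious, death within 30 days of last dose) carry no drug filter.

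Later in the same section, the summaries by system organ class and preferred term include "treatment-related adverse events (OPZ, POM, DEX, and study drug") and "TEAEs that led to permanent discontinuation of study drug (OPZ, POM, DEX and study treatment").

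In the protocol, section 5.1.3 states: "Study drug is defined as the combination of oprozomib, pomalidomide, and dexamethasone". Section 13.2 asks the investigator, for a possibly drug-related event, to "assess its relationship to each of the study drugs: oprozomib, pomalidomide, and dexamethasone". Section 14.5.1.1 lists the same three agents as study treatment when it defines the safety population.

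**The concern.** The regimen under study is a triplet, and evaluating the safety and tolerability of that combination is a primary objective (SAP 2.3.1). The three restricted rows are where the abbreviated report gives its summary-level rates of related events and of discontinuations due to events. Programmed as written, they describe two of the three drugs while their labels speak of treatment-related events and of study drug.

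Two things are at stake. The first is a one-directional error: dropping a drug from an any-drug count cannot raise it, so any error makes the regimen look better tolerated than it was. The second is reconciliation: one report would hold two meanings of treatment-related and two of discontinuation of study drug, and the overall rows might not agree with the tables beneath them.

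**Working it through.** There is no sample-size or power figure to reproduce. The check compares drug lists, followed by simple arithmetic on what one subject is worth.

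**Step 1: count the rows of the overall summary (SAP 7.6.1).**

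| Row | Content | Drugs named |
|---|---|---|
| 1 | Any TEAE | none (unfiltered) |
| 2 | Treatment-related TEAE | OPZ, DEX |
| 3 | TEAE of grade 3 or higher | none (unfiltered) |
| 4 | Treatment-related, grade 3 or higher | OPZ, DEX |
| 5 | Serious AE | none (unfiltered) |
| 6 | TEAE leading to discontinuation of study drug | OPZ, DEX |
| 7 | TEAE leading to discontinuation of OPZ | OPZ |
| 8 | Death within 30 days of last dose | none (unfiltered) |

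Rows limited to OPZ or DEX: 3 of 8. Rows naming POM: 0 of 8. Of the seven summaries by organ class or preferred term in the same section, the two that deal with relatedness and with discontinuation both name POM.

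**Step 2: look for a reason.** SAP section 1 says that changes to analyses planned in the protocol will be documented in the SAP. None is recorded for leaving out pomalidomide. Elsewhere the SAP treats all three agents alike: baseline is set relative to the first dose of any of them (5.3), and exposure is summarised for each (7.4.1). A difference in protocol version does not explain it either. The SAP is written against Amendment 2, and that amendment's change log shows the study-drug definition being added at that point.

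**Step 3: ask whether pomalidomide-only events can arise.** The protocol provides for them:

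- Table 14 has a row for other nonhematologic toxicity judged pomalidomide-related, with oprozomib kept at full dose.
- Section 10.4.2.1.1 includes an instruction under which pomalidomide itself is discontinued.
- Section 10.1 says "subjects who permanently discontinue pomalidomide or oprozomib may continue on study".
- Section 10.5 recognises rash attributed specifically to pomalidomide.

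**Step 4: direction.** Let A be the subjects with an event related to OPZ or DEX, and B the subjects with an event related to OPZ, POM or DEX. Every member of A is in B, so |A| ≤ |B|. The gap k = |B| − |A| is the number of subjects whose related events are attributed to POM alone. The same holds for row 4 with grade 3 or higher events, and for row 6 with subjects who stopped only POM because of an event. Each row is therefore too low or unchanged, never too high.

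**Step 5: what one subject is worth.** SAP 7.1 presents results by schedule and dose group, with some summaries for the combined recommended-dose cohort. SAP 2.4 plans 6 + 20 = 26 subjects in that combined group.

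- Group of 26: 1/26 = 3.8 percentage points per missed subject
- Cohort of 6: 1/6 = 16.7 percentage points per missed subject

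Neither document gives k or any rate from which it could be derived.

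**The case against.** The strongest reply is that nothing disappears from the report. Pomalidomide-only events still enter the four unfiltered rows, the related-event and discontinuation tables by organ class and preferred term, the grade 3 or higher laboratory summary where they are laboratory findings, and the subject listings. Dose escalation rests on the safety committee's review of DLTs, not on these rows. Part 2 had already been cancelled, and this SAP serves only an abbreviated report. All of that is true. It limits the consequence to three rows of one table, but it does not make those rows right.

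A second reply is that the protocol's explicit definition of study drug sits in the DLT text, and that protocol 14.5.3 prescribes no particular relatedness or discontinuation row. That is also true. However, sections 13.2 and 14.5.1.1 apply the same three-drug meaning to adverse-event causality and to the safety population, and the inconsistency inside SAP 7.6.1 stands without the protocol.

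A third reply is that the percentage-point figures are only 1/n. That is correct: they show how sensitive small groups are and predict nothing. The 26 is itself conditional, because 20 is a minimum and the recommended dose may differ from the MTD.

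Finally, the detailed discontinuation table lists study treatment as a category separate from the three drugs and does not define it. Adding POM to row 6 gives an any-drug count, which need not equal a count of subjects who stopped all treatment. That point stands and is dealt with in the fix. It does not rescue the existing row, whose wording is already an any-drug count with one drug missing.

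**Conclusion.** The concern holds. Three of the eight rows apply a two-drug rule where the protocol and the rest of the same SAP section use three drugs, and no reason is given. This is a wrong rule rather than missing detail: a programmer following it would exclude pomalidomide-only attributions and pomalidomide-only discontinuations.

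The direction of any error is certain. Its size is unknown and could be zero, because it depends entirely on how many subjects have only pomalidomide-attributed events or stop only pomalidomide. No endpoint definition or escalation decision depends on these rows. The point should be corrected before the report is produced, but its reach is the overall summary table and its agreement with the detailed tables.

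**What to change.** In SAP 7.6.1, replace the limit to OPZ or DEX with OPZ, POM or DEX in the three rows: treatment-related TEAE, treatment-related TEAE of grade 3 or higher, and TEAE leading to discontinuation of study drug.

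Two small additions would help. State that the discontinuation row counts subjects who stopped any one of the three drugs because of an event, and define the study-treatment category in the detailed discontinuation table, so that readers know which counts should agree. Optionally, add a row for events leading to discontinuation of pomalidomide beside the existing oprozomib row.

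The cost is a wording change and a minor programming change. Causality for each drug is already requested by protocol 13.2, and pomalidomide is already needed for the detailed tables, so no new data are required. The reported related-event and discontinuation rates will stay the same or rise.

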7.6.2 Laboratory Data

All available laboratory results will be included in the subject data listings.

Selected laboratory test results will be assigned toxicity grades using CTCAE 4.03. A summary of post-baseline grade 3 or higher laboratory toxicities will be provided. The laboratory parameters of interest for these summaries are:

| Hematology (all decrease) | Serum Chemistry (increase except where noted) | |
|----------------------------------|--|--------------------------------|
| Hemoglobin | ALT | Albumin |
| Platelets | AST | Uric Acid |
| WBC | Alkaline Phosphatase | Sodium (increase, decrease) |
| Neutrophils (absolute) | Total Bilirubin | Phosphorus (decrease) |
| Lymphocytes (absolute) | Creatinine | Potassium (increase, decrease) |
| | Calcium (increase, decrease) | Magnesium (increase, decrease) |
| | Glucose (increase, decrease) | |

7.6.3 Vital Signs and Weight

Vital sign results including blood pressure, pulse, and temperature will be included in the subject data listings.

7.6.4 12-Lead Electrocardiogram

Maximum post-baseline and maximum increase from baseline categories of corrected QT interval results will be summarized.

7.6.5 Prior and Concomitant Medications

All prior and concomitant medications will be coded using WHO Drug Dictionary. Concomitant medications are defined as medications with start date or end date on or after the date of first dose and before the date of the last dose + 30 days or are ongoing at the time of first dose. Prior medications are defined as medications with a stop date before the date of first dose.

Concomitant medications will be summarized by generic name.

7.6.6 Protocol Deviations

Protocol deviations will be included in the subject data listings. Major protocol deviations will be either captured on the designated eCRF (e.g., eligibility violations) or identified through data review and surveillance. Statistical/Analytical Issues

7.7 Handling of Dropouts or Missing Data

The handling of dropouts and missing disease status assessments for the efficacy variables is described in their definitions.

Missing or partially missing dates will not be imputed at data level. However, assumptions for missing or partially missing dates for important variables will be made to allow inclusion of appropriate data records in the analyses.

If a medication date or time is missing or partially missing, so it cannot be determined whether it was taken prior or concomitantly, it will be considered as a prior, concomitant, and a post-treatment medication.

If the partial AE onset date information does not indicate whether the AE started prior to treatment or after the TEAE period, the AE will be classified as TEAEs.

If the start day of subsequent anti-cancer therapy is missing, it will be assumed to be the first day of the month.

7.8 Interim Analysis and Data Monitoring

The CSRC will review the clinical data of each dose cohort after three subjects have been treated for at least one cycle during phase 1 of the study. Based on the number of subjects with dose-limiting toxicity, escalation to the next higher OPZ dose may occur, the cohort may be expanded to six subjects, or dosing at that dose level may stop and the next-lower dose cohort may be expanded. The committee must agree that dose escalation to the next cohort is appropriate before it proceeds.
